6.2.2. Absolute Bioavailability

All listings and analyses of absolute bioavailability will use the PK Parameter population (as defined in [Section 4](#)).

*Natural log transformed $AUC_{inf}(dn)$ (if data permit, otherwise $AUC_{last}(dn)$) from **Period 2** will be analyzed using a mixed effect model (as defined in [Section 5.2.3](#)) with treatment as a fixed effect and participant as a random effect. Estimates of the adjusted (least squares) mean differences (Test-Reference) and the corresponding 90% confidence interval will be obtained from the model. The adjusted mean differences and 90% confidence intervals for the differences will be exponentiated to provide estimates of the ratio of adjusted geometric means (Test/Reference) and 90% confidence interval for the ratio where IV [¹⁴C]PF-07081532 is the reference formulation and unlabeled oral PF-07081532 is the test formulation.*

Individual oral bioavailability (F) values (as defined in [Section 3.2.1](#)) will also be listed.

A box plot of the individual $AUC_{inf}(dn)$ (if data permit, otherwise $AUC_{last}(dn)$) values used to calculate such bioavailability from Period 2 only will be produced with a separate box and whiskers for each analyte and treatment (IV vs PO), which will include the geometric means for each analyte overlaid.

The above will be conducted for $AUC_{last}(dn)$ regardless, but will only be formally reported if $AUC_{inf}(dn)$ data do not permit sufficient estimation of F.

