- b. Assessment of risk for, symptoms of or testing for COVID-19 may be performed at screening, admission to the CRU and/or at other times during the study at investigator discretion and according to local site policies.
- c. Complete physical examination, including height and weight, will be conducted at screening or admission of Period 1 only; brief physical exam at other time points, for findings during previous PE or new/open AEs, at investigator discretion.
- d. Procedures to be performed on the day of discharge *only*. (see also [Section 4.1](#)).
- e. Meals will be served throughout inpatient stay, as described in [Section 5.3.2](#). Standardized meals to be served on Day 1.

CCI

- g. Samples to be collected up to the morning of Day 7 only.
- h. If not collected on the designated collection day, collect at the next available time point when biospecimens are being collected in conjunction with a participant visit.
- i. "Blank" pre-dose urine sample to be collected within the 24 hours prior to dosing. Following oral dosing, each urine void to be collected across intervals of 0-12 hours, 12-24 hours, and each subsequent 24 hours interval up to discharge from Period 1, as described in [Section 8.5.2](#).
- j. "Blank" fecal sample to be collected from at least 1 bowel movement within the 48 hours prior to dosing, which may be collected from home. Following oral dosing, all feces excreted will be collected across each 24 hours interval up to discharge from Period 1, as described in [Section 8.5.3](#).

CCI

Table 2. Schedule of Activities From Period 2, Day -1 Through Follow-up

Visit Identifier	Period 2																		FU*	ET		
Day	-1	1										2				3	4	5	6	7b	28-35	
Hours Relative to Oral Dosing of Unlabeled PF-07081532		0	0.5	1	1.17	1.25	1.33	1.5	2	4	6	8	10	12	15	24	36	48	72	96	120	144
Hours Relative to Dosing of (¹⁴ C)PF-07081532 (IV infusion start)			0	0.17	0.25	0.33	0.5	1	3	5	7	9	11	14	23	35	47	71	95	119	143	
Inpatient stay at CRU		X																				
COVID-19 testing/risk assessment ^b																						
Physical examination ^b	X																			X		X
(Update.)dmg/alcohol/tobacco use	X																				X	X
Review prior & concomitant medications	X																			X	X	
Supine 12-lead ECG		X																		X		X
Supine vital signs (blood pressure and pulse rate)		X																		X		X
Serious and non-serious adverse event monitoring	X																			X	X	X
Standard meals ^b		X													X		X					

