Period 1 of the study is designed to evaluate the metabolic fate and extent of excretion of PF-07081532 following 30 mg dose (250 nCi) via the intended clinical route of administration (oral) of [¹⁴C]PF-07081532. In order to assess the metabolic fate of [¹⁴C]PF-07081532, metabolites of [¹⁴C]PF-07081532 circulating in plasma and eliminated in urine and feces following oral administration will be determined using AMS and UPLC-HRMS. Additionally, extent of excretion will be determined by recovery of total radioactivity excreted in urine and feces. Lastly, plasma PK of PF-07081532 will be compared to total radioactivity PK as an additional way to quantify circulating metabolites. Based on the half-life observed after single dose administration in Study C3991001 (mean ranging between 18 and 21 hours with individual values up to 29 hours), PF-07081532 is expected to be eliminated from plasma by Day 7 (144 hours). Additional 14 days of permitted extended stay in Period 1 (up to Day 21), based on predefined discharging criteria (see [Section 4.1](#)), is expected to be adequate to enable almost complete recovery of radioactivity in excreta and allow excretion of any potential metabolites with longer half-lives.

Samples for measurement of radioactivity in [CCI](#) will be collected in Period 1 at timepoints specified in the [SoA](#). These samples may be assayed at sponsor's discretion to support any potential investigations in case of less than expected recovery of total radioactivity via urine and feces. Results from the analysis of these samples, if performed, may not be included in the CSR.

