8.5.1.4. Period 2 Plasma for Analysis of Oral, Unlabeled PF-07081532, Using LC/MS/MS

For **Period 2**, blood samples (3 mL) to provide approximately 1.2 mL plasma for concentrations of unlabeled PF-07081532 will be collected into appropriately labeled tubes containing K₂EDTA at times specified in the [SoA](#).

Samples for unlabeled PF-07081532 will be analyzed using a validated LC/MS/MS analytical method in compliance with Pfizer standard operating procedures.

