8.5.1.5. Period 2 Plasma for Analysis of IV [¹⁴C]PF-07081532 Using AMS and UPLC-HRMS

During study **Period 2**, blood samples (4 mL) to provide approximately 1.6 mL plasma will be collected as specified in the [SoA](#) following IV administration of [¹⁴C]PF-07081532, into appropriately labeled tubes containing K₂EDTA. Samples from **Period 2** will be analyzed for [¹⁴C]PF-07081532 using a validated quantitative AMS method following chromatographic separation of the parent drug.

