9.3.3. Secondary Endpoint(s) Analysis

9.3.3.1. Pharmacokinetic Parameters

9.3.3.1.1. Plasma

- For **Period 1**, following a single oral administration of [¹⁴C]PF-07081532, oral PK parameters for total [¹⁴C] radioactivity will be derived from the concentration equivalent-time profiles, where appropriate. Additionally, PK parameters for PF-07081532 will be derived from the concentration-time profiles based on LC/MS/MS analysis of plasma samples.
- For **Period 2**, following a single oral dose of unlabeled PF-07081532, PK parameters for PF-07081532 will be derived from the concentration-time profiles based on LC/MS/MS analysis of plasma samples (note that this reflects a tertiary endpoint and as such is also listed under [Section 9.3.4](#)).

- For **Period 2**, following a single IV microdose dose of [¹⁴C]PF-07081532 at 1 hour post oral dose, IV plasma PK parameters of [¹⁴C]PF-07081532 will be derived from plasma radioactivity concentration-time profiles following chromatographic separation of [¹⁴C]PF-07081532.

Parameter	Definition	Method of Determination
AUC _{last}	Area under the plasma concentration-time profile from time 0 to time of the last quantifiable concentration (C _{last})	Linear/Log trapezoidal rule
AUC _{last(dn)}	Dose-normalized AUC _{last} , in Period 2 only	AUC _{last} /Dose
AUC _{inf} ^a	Area under the plasma concentration-time profile from time zero extrapolated to infinite time	AUC _{last} + (C _{last} * ^a /k _{el}), where C _{last} * is the predicted plasma concentration at the last quantifiable time point estimated from the log-linear regression analysis, where k _{el} is the terminal phase rate constant calculated by a linear regression of the log-linear concentration-time curve. Only those data points judged to describe the terminal log-linear decline will be used in the regression
AUC _{inf(dn)} ^a	Dose-normalized area under the plasma concentration-time profile from time zero extrapolated to infinite time, in Period 2 only	AUC _{inf} /Dose
C _{max}	Maximum plasma concentration	Observed directly from data
C _{max(dn)}	Dose-normalized maximum plasma concentration, in Period 2 only	C _{max} /Dose
T _{max}	Time for C _{max}	Observed directly from data as time of first occurrence
t _{1/2} ^a	Terminal elimination half-life	Log _e (2)/k _{el}
CL ^a (IV)	CL: systemic clearance following IV administration	Dose/AUC _{inf}
MRT ^a (IV)	Mean residence time	AUMC _{inf} /AUC _{inf} - (infusion time/2)

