9.3.3.1.2. Absolute Bioavailability

F will be estimated (in **Period 2** only) as the ratio of adjusted geometric means of dose-normalized AUC_{inf} (if data permit, otherwise AUC_{last}) following oral, unlabeled, PF-07081532 and IV, [¹⁴C]PF-07081532 which is equivalent to the following equation:

$$F = [PF-07081532_AUC_{po}/PF-07081532_AUC_{iv}]*[PF-07081532_Dose_{iv}/PF-07081532_Dose_{po}]$$

Natural log transformed $AUC_{inf}(dn)$ (if data permit, otherwise $AUC_{last}(dn)$) from **Period 2** will be analyzed using a mixed effect model with treatment as a fixed effect and participant as a random effect. Estimates of the adjusted (least squares) mean differences (Test-Reference) and the corresponding 90% confidence interval will be obtained from the model. The adjusted mean differences and 90% confidence intervals for the differences will be exponentiated to provide estimates of the ratio of adjusted geometric means (Test/Reference) and 90% confidence interval for the ratio where IV [¹⁴C]PF-07081532 is the reference formulation and unlabeled oral PF-07081532 is the test formulation.

Summary plasma concentrations (dose-normalized) of orally administered PF-07081532 and IV administered [¹⁴C]PF-07081532 in Period 2 will be presented in the same plot by route of administration using nominal sampling times.

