5.3.1. Plasma Pharmacokinetic Parameters

Actual PK sampling times will be used in the derivation of plasma PK parameters.

If a PK parameter cannot be derived from a participant's concentration data, the parameter will be coded as NC (i.e. not calculated). (Note that NC values will not be generated beyond the day that a participant discontinues.)

In summary tables, statistics will be calculated by setting NC values to missing; and statistics will be presented for a particular treatment group/analyte with ≥ 3 evaluable measurements.

Note: If $N < 3$ evaluable measurements, only mean, median and range will be provided in summary statistics.

For statistical analyses (i.e. mixed effect model), PK parameters coded as NC will also be set to missing; and analyses will not be performed for a particular parameter if more than 50% of the data are NC.

If an individual participant has a known biased estimate of a plasma PK parameter (due for example to an unexpected event such as vomiting before all the compound is adequately

absorbed in the body), this will be footnoted in summary tables and will not be included in the calculation of summary statistics or statistical analyses.

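### The AUClast fallback for absolute bioavailability lets the two routes end at different times; a common-window AUC would remove most of the resulting shift in F

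*SAP*

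**What the plan says.** Protocol 9.3.3.1.2 bases F on "dose-normalized AUC_{inf} (if data permit, otherwise AUC_{last}) following oral, unlabeled, PF-07081532 and IV" dosing with the labelled drug in Period 2. SAP 6.2.2 runs the AUClast(dn) analysis in every case but reports it formally only if the AUCinf(dn) "data do not permit sufficient estimation of F". The parameter table in Protocol 9.3.3.1.1 defines AUClast as "Area under the plasma concentration-time profile from time 0 to time of the last quantifiable concentration", so the end point belongs to each profile separately.

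Oral samples "will be analyzed using a validated LC/MS/MS analytical method" (Protocol 8.5.1.4). IV samples are measured "using a validated quantitative AMS method following chromatographic separation of the parent drug" (Protocol 8.5.1.5). Neither document gives a quantification limit for either assay.

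Scheduled sampling is matched. In Protocol Table 2 the row "Hours Relative to Oral Dosing of Unlabeled PF-07081532" runs to 144 h, and the same draws are 143 h after the start of infusion.

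The only numerical rule on unusable parameters is in SAP 5.3.1: "analyses will not be performed for a particular parameter if more than 50% of the data are NC". It does not address unequal end times. There is no limit on the extrapolated percentage of AUCinf, which is only listed (SAP 6.2.1).

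**The concern.** Matched scheduled draws do not guarantee matched quantifiable draws. Two assays with separate limits, applied after 30 mg and 100 µg, can lose the drug at different times. If they do, the AUClast ratio does not estimate F. It estimates F multiplied by the share of the oral AUC captured and divided by the share of the IV AUC captured.

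The shift is systematic, so the mixed model's 90% interval does not reflect it. F is a secondary endpoint, and Protocol 4.2 intends to read F together with Fa to determine the first-pass effect, so an error in F would carry into that reading.

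The plan already accepts the principle for Fa: Protocol 9.3.3.1.3.2 and SAP 3.2.2 cut Period 1 urine at Day 7 so that the two collections cover the same duration. The F fallback is the same kind of route-to-route ratio and has no such rule. It is also most likely to be needed when a profile ends early, which is when unequal windows matter.

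**Working it through.** **Inputs from the documents.** Half-life "mean ranging between 18 and 21 hours with individual values up to 29 hours" (Protocol 4.2), taken as 18, 21 and 29 h. Late draws (Protocol Table 2): oral 24, 36, 48, 72, 96, 120, 144 h; IV 23, 35, 47, 71, 95, 119, 143 h, each after its own dose. Oral Tmax about 1 h; infusion 15 min (Protocol 4.1).

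**Assumptions.** The actual end times (no quantification limits are given), mono-exponential decline, and the same half-life by both routes.

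**Step 1: the plan's own figure.** Protocol 4.2 expects elimination from plasma by 144 h. The remaining fraction is exp(−ln 2 × 144/t½). That is 8.0, 6.9 and 5.0 half-lives, leaving 0.4%, 0.9% and 3.2%. The statement is consistent with the half-lives.

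**Step 2: the bias.** With k = ln 2/t½,

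reported F / true F = (1 − exp(−k·t_oral)) / (1 − exp(−k·t_IV)).

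Example, t½ 21 h, oral to 144 h, IV to 71 h: k = 0.0330, and (1 − 0.0086)/(1 − 0.0960) = 0.9914/0.9040 = 1.097.

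| Oral ends | IV ends | 18 h | 21 h | 29 h |
|---|---|---|---|---|
| 144 h | 143 h | 1.0002 | 1.0003 | 1.0008 |
| 144 h | 119 h (one draw early) | 1.006 | 1.011 | 1.028 |
| 144 h | 95 h (two early) | 1.022 | 1.036 | 1.079 |
| 144 h | 71 h (three early) | 1.065 | 1.097 | 1.185 |
| 144 h | 47 h (four early) | 1.191 | 1.258 | 1.434 |
| 72 h | 143 h | 0.941 | 0.915 | 0.849 |

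**Step 3: only some participants affected.** F is a ratio of geometric means, so with m of 6 affected the factor is raised to the power m/6.

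| Affected | IV ends | 18 h | 21 h | 29 h |
|---|---|---|---|---|
| 4 of 6 | 71 h | 1.043 | 1.063 | 1.120 |
| 4 of 6 | 47 h | 1.124 | 1.165 | 1.272 |
| 2 of 6 | 71 h | 1.021 | 1.031 | 1.058 |
| 2 of 6 | 47 h | 1.060 | 1.080 | 1.128 |

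**Step 4: would AUCinf still be usable?** The share of the IV AUC left to extrapolate is exp(−k·t_IV): 6.5/9.6/18.3% at 71 h and 16.4/21.2/32.5% at 47 h.

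**Step 5: other models.** A one-compartment model with first-order absorption and a 15-minute infusion gives almost the same factors (IV to 71 h: 1.066/1.097/1.186). Raising Tmax to 4 h (assumed) moves them by less than 1 point. The linear/log trapezoidal rule on the Table 2 times agrees within about 0.5 points. A two-compartment model with the terminal phase carrying 50–90% of the AUC gives smaller shifts: 1.03–1.16 three draws early and 1.09–1.37 four draws early.

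**Step 6: what remains after matching windows** (one-compartment model, range over the three half-lives).

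| Window | Tmax | 23 h | 47 h | 71 h |
|---|---|---|---|---|
| Equal time from own dose | 1 h | 0.998 | 0.999 | 1.000 |
| Equal time from own dose | 4 h | 0.968–0.969 | 0.989–0.991 | 0.995–0.997 |
| Same draw (oral = IV + 1 h) | 1 h | 1.025–1.031 | 1.007–1.011 | 1.002–1.005 |

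**The case against.** Two things must happen together: AUCinf must be judged inadequate, and one route must lose several draws. The documents point the other way. Protocol 4.2 expects elimination by 144 h and Protocol 4.3 expects adequate AMS sensitivity. This stands, and without quantification limits the probability cannot be computed.

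The largest shifts assume a clean mono-exponential decline, which is the case in which a terminal slope can be fitted and AUCinf used. This stands largely for 71 h. It is weaker for 47 h, where 16–33% of the IV AUC is unobserved. If AUCinf fails because the terminal phase is ill-defined, the mono-exponential sizes are only a guide, and the two-compartment range is the fairer one.

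The 29 h figures apply the largest individual value to a whole group, so they are an upper case. The 2-of-6 row is largely academic if a short profile means AUCinf is not calculated: 2/6 is 33%, below the 50% bar, so the AUCinf analysis would proceed. The 4-of-6 row (67%) is above it.

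Listings of concentrations and individual F values, and the overlaid profiles in SAP 6.2.1, would make a mismatch visible. They would not correct the reported ratio. Finally, no hypothesis or decision rule depends on F (SAP 5.1), and the first-pass rationale in Protocol 4.2 is written in terms of AUCinf. Both are true, and they limit the weight of the point.

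**Conclusion.** The concern holds as a minor, conditional point. Under the stated fallback, F is nearly unbiased if both routes are quantifiable to the last draw, and it moves by less than 3% if one draw is lost. If the IV route ends three draws early in everyone, F is overstated by about 7–10% at the mean half-lives (19% at 29 h). At four draws early the figures are 19–26% (43% at 29 h). If the oral route ends at 72 h instead, F is understated by 6–8% (15% at 29 h).

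These sizes rest on assumed end times and mono-exponential decline; a two-compartment profile reduces them without removing them. AUCinf will probably be usable, in which case the issue does not arise.

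**What to change.** In SAP 6.2.2, keep AUCinf(dn) as the main metric and keep the 50% rule in SAP 5.3.1. Replace the AUClast(dn) fallback for F with dose-normalised AUC(0–tc) for both routes. Within each participant, tc is the shorter of the two last quantifiable elapsed times, each counted from its own origin (oral dose; start of infusion).

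Because late sampling times differ by 1 h between routes, obtain the longer profile's concentration at tc by log-linear interpolation. If IV ends at 71 h, for example, the oral value at 71 h comes from the 48 h and 72 h samples. State also whether the switch to the fallback is made per participant or for the whole analysis, since the text does not say.

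A simpler alternative is to cut both profiles at the same draw, which needs no interpolation. It leaves −0.1 to +1.1% at 47 h or later, but up to +3.1% at 23 h with Tmax 1 h.

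The cost is SAP wording, one derived parameter and an entry in SAP 2.1, with no new samples. Protocol section 9 lets the SAP modify the outlined analysis and calls for an amendment only for major changes to primary endpoints; F is secondary. The downside is that some quantifiable data are set aside and absorption delay slightly understates F. With Tmax 1 h this is 0.02–0.11% for tc of 35–71 h and 0.2% at 23 h. If Tmax were 4 h (assumed), it would reach 1.8% at 35 h and 3.2% at 23 h.

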6.2.3. Fraction Absorbed

All listings and analyses of absolute bioavailability will use the PK Parameter population (as defined in [Section 4](#)).

Total radioactivity excreted in urine as absolute values (Total ¹⁴C_Urine_PO and Total ¹⁴C_Urine_IV) and expressed as percent of [¹⁴C] dose (% ¹⁴C_Urine_PO and % ¹⁴C_Urine_IV) as defined in [Section 3.2.2](#) will be listed and summarized descriptively by period. Summaries will include: N; arithmetic mean; median; cv%; standard deviation; minimum; maximum; geometric mean; and geometric cv%.

Natural log transformed % [¹⁴C]_Urine_PO_Trunc (if data permit) from Period 1 and % [¹⁴C]_Urine_IV (if data permit) from Period 2 will be analyzed using a mixed effect

model (as defined in [Section 5.2.3](#)) with treatment as a fixed effect and participant as a random effect.

Estimates of the adjusted (least squares) mean differences (Test-Reference) and the corresponding 90% confidence interval will be obtained from the model. The adjusted mean differences and 90% confidence intervals for the differences will be exponentiated to provide estimates of the ratio of adjusted geometric means (Test/Reference) and 90% confidence interval for the ratio where IV [¹⁴C]PF-07081532 is the reference formulation and oral [¹⁴C]PF-07081532 is the test formulation.

The individual mean fraction absorbed (Fa) values (as defined in [Section 3.2.2](#)) will also be listed.

A box plot of the individual values of % ¹⁴C_Urine_PO_Trunc and % ¹⁴C_Urine_IV in Periods 1 and 2, respectively, will be produced with a separate box and whiskers for each period, which will include the geometric means for each period overlaid.

Absolute radioactivity concentration levels excreted in urine at each time interval for both periods will also be listed only.

6.3. Other Endpoint(s)

6.3.1. Cumulative recovery of radioactivity excreted in Urine, Feces and Combined

[figure not shown]
Cumulative recovery of radioactivity excreted in urine, feces and both routes combined, expressed as a percentage of the administered dose of [14C]PF-07081532 up to and including each time interval, will be listed, summarized, plotted and detailed in a separate report provided by ICON and will be summarized within the CSR as part of the extent of Excretion analysis.

6.3.2. Plasma PK parameters of PF-07081532 in Period 2

[figure not shown]
Plasma PK parameters of PF-07081532 in Period 2 as described in [Section 3.2.1](#) will be listed and summarized descriptively (as outlined in Table 3 in [Section 6.2.1](#)) for participants in the PK analysis set (as defined in [Section 4](#)). Missing values will be handled as detailed in [Section 5.3](#).

A similar set of outputs as provided in [Section 6.2.1](#) will be produced for the individual plasma concentration data of PF-07081532 in Period 2 PK Concentration Set (as defined in [Section 4](#)).

CCI

CCI

6.3.5. Banked Biospecimens

Banked biospecimens will be collected and retained for future analyses, but will not be analyzed specifically for this study and will not be included in the CSR.

6.4. Subset Analyses

No subset analyses will be performed.

6.5. Baseline and Other Summaries and Analyses

Data will be reported in accordance with the sponsor reporting standards.

6.5.1. Baseline Summaries

Demographics data (age, gender, race, ethnicity, weight, body mass index and height) will be summarized as outlined in [Section 5.2.1](#) and [Section 5.2.2](#) as applicable for all participants.

6.5.2. Study Conduct and Participant Disposition

Participant evaluation groups will show end of study participant disposition by treatment and will show which participants were analyzed for pharmacokinetics (plasma and urine, separately), taste assessment and for safety, which may not be produced in one table. Frequency counts and percentages will be supplied for participant discontinuation(s) by treatment.

